## **2 SCHEDULE OF ACTIVITIES**

Study assessments and procedures are shown in [Table 2-1](#), [Table 2-2](#), [Table 2-3](#), [Table 2-4](#), and [Table 2-5](#).

**Table 2-1: Screening Schedule of Activities for All Study Parts**

Procedure	Screening Visit (Days -28 to -1)	Notes
Eligibility Assessments		
Informed Consent	X	A participant is considered enrolled only when a protocol-specific ICF is signed.
IRT Participant Assignment	X	After the participants meet all eligibility criteria, sites will use IRT for participant number assignment. Subsequent visits will be registered into the IRT system for drug supply (see Section 5.1.1 ).
Inclusion/Exclusion Criteria	X	See Section 6.1 and Section 6.2 .
Medical History	X	Include any toxicities or allergy related to previous treatments and tumor characteristics (eg, mutation status, receptor status, viral status, if available). All medical history relevant to the disease under study, and COVID-19 vaccines more than 30 days prior to first study treatment.
Prior Cancer Therapies	X	
Concomitant Medications	X	Within 14 days prior to randomization/treatment assignment. Vaccine use within 30 days prior to first study treatment.
ECOG Performance Status	X	
Safety Assessments		
PE	X	If the screening PE is performed within 72 hours prior to dosing on Day 1, then a single examination may count as both the screening and predose evaluation on C1D1.
Physical Measurements	X	Includes height and weight.
Vital Signs	X	Includes body temperature, respiratory rate, and seated/supine blood pressure and heart rate. Blood pressure and heart rate should be measured after the participant has been resting quietly for at least 5 minutes.
Oxygen Saturation	X	Pulse oximetry collected at rest.
ECG	X	ECGs should be recorded after the participant has been supine for at least 5 minutes and prior to blood draws. Screening ECG is to be collected as a single reading (see Section 9.1.3 ).
Laboratory Tests	X	See Clinical Laboratory Assessments in Section 9.1.4 and Table 9.1.4-1 . There will be a minus-72-hour window from C1D1 during screening for the collection of laboratory tests.
Urinalysis	X	Microscopic urine reflex only for urinalysis positive for blood/protein/leukocytes.

**Table 2-1: Screening Schedule of Activities for All Study Parts**

Procedure	Screening Visit (Days -28 to -1)	Notes
Serology	X	Includes hepatitis C Ab, hepatitis B surface antigen, and HIV-1 and HIV-2 Ab (see Section 9.1.4 and Table 9.1.4-1 ).
Pregnancy Test	X	For WOCBP only. Serum to be collected at screening and within 24 hours prior to dosing on Day 1 of each treatment cycle. Serum pregnancy test may be taken on the first day of treatment, provided results are available prior to starting study therapy. If pregnancy test is taken within 24 hours of dosing (C1D1), a further pregnancy test is not required.
FSH	X	Women only, as needed to document postmenopausal status.
Adverse Event Reporting		
Assessment of Signs/Symptoms/ Clinical Complaints	X	
Monitor for SAEs	X	All SAEs must be collected from the date of participant's written consent until 100 days after discontinuation of dosing.  All AEs (SAEs or nonserious AEs) associated with SARS-CoV-2 infection collected from time of consent.
Tumor Assessments		
Body Imaging	X	Refer to Imaging Assessment details in Section 9.3.1 . CT and MRI scans should be acquired with a slice thickness of 5 mm or less with no intervening gap (contiguous). Every attempt should be made to image each participant using an identical acquisition protocol on the same scanner for all imaging timepoints.
Brain Imaging	X	MRI without and with contrast of the brain required at screening only if participant is symptomatic or has history of brain metastasis and has not had brain imaging within 30 days of anticipated first study drug administration. CT of the brain without and with contrast may be performed if MRI is contraindicated. Refer to Imaging Assessment details in Section 9.3.1 . CT and MRI scans should be acquired with a slice thickness of 5 mm or less with no intervening gap (contiguous). Every attempt should be made to image each participant using an identical acquisition protocol on the same scanner for all imaging timepoints.

**Table 2-1: Screening Schedule of Activities for All Study Parts**

Procedure	Screening Visit (Days -28 to -1)	Notes
Bone Scan	X	Required for participants with prostate cancer for evaluation of bone disease; otherwise, as clinically indicated. Refer to Imaging Assessment details in Section 9.3.1 . Every attempt should be made to image each participant using an identical acquisition protocol on the same scanner for all imaging timepoints.
Clinical Treatment Supplies		
Dispense Study Treatment	X	Study treatments (BMS-986218, ipilimumab, and nivolumab) to be supplied by BMS and in assigned vials per IRT (see Section 5.1.1 , Table 2-2 , Table 2-3 , and Table 2-4 ).

Abbreviations: Ab = antibody; AE = adverse event; BMS = Bristol-Myers Squibb; C1D1 = Cycle 1 Day 1; CT = computed tomography; [REDACTED] ECG = electrocardiogram; ECOG = Eastern Cooperative Oncology Group; FSH = follicle stimulating hormone; HBV = hepatitis B virus; HCV = hepatitis C virus; HIV = human immunodeficiency virus; ICF = informed consent form; IRT = Interactive Response Technology; MRI = magnetic resonance imaging; [REDACTED] [REDACTED] PE = physical examination; RNA = ribonucleic acid; SAE = serious adverse events; SARS-CoV-2 = severe acute respiratory syndrome coronavirus 2; WOCBP = women of childbearing potential.

**Table 2-2:**

**On-Treatment - Schedule of Activities for Q4W Dosing Schedules in BMS-986218 Monotherapy Escalation (Part 1A), Safety Evaluation of Combination Doses of BMS-986218 with Nivolumab (Part 1B), Randomized BMS-986218 Monotherapy Cohort Expansion in Cutaneous Melanoma (Part 2A), Randomized BMS-986218 Monotherapy Cohort Expansion (Part 2B), and Combination Cohort Expansions (Part 2C and Part 2D)**

Procedure	Cycle 1 (28 Days in Length) (Visit Window $\pm$ 2 Days, except for C1D1)				Cycle 2 (28 Days in Length) (Visit Window $\pm$ 2 Days)				Cycles 3 and Beyond (Each Cycle 28 Days in Length) (Visit Window $\pm$ 2 Days)	EOT a,b	Notes		
	DLT Period is Cycles 1 and 2												
	D1	D8	D15	D22	D1	D8	D15	D22	D1				
Safety Assessments													
ECOG Performance Status	X				X				X	X			
PE	X				X				X	X			
Symptom Directed PE		X	X	X		X	X	X					
Weight	X				X				X	X			
Vital Signs	X	X	X	X	X	X	X	X	X	X	
For BMS-986218, vital signs will be obtained within 30 minutes before the start of the infusion and then every 15 minutes (<math>\pm</math> 5 minutes) from the start of the infusion until 60 minutes after completion of the infusion for the first 3 doses of study treatment on C1D1, C2D1, and C3D1. For all cycles after cycle 3, vital signs and oxygen saturation are to be taken before the infusion and at the end of each infusion.
 
For nivolumab, vital signs will be obtained within 30 minutes before the start of the infusion and then every 30 minutes (<math>\pm</math> 5 minutes) from the start
		

**Table 2-2:**

**On-Treatment - Schedule of Activities for Q4W Dosing Schedules in BMS-986218 Monotherapy Escalation (Part 1A), Safety Evaluation of Combination Doses of BMS-986218 with Nivolumab (Part 1B), Randomized BMS-986218 Monotherapy Cohort Expansion in Cutaneous Melanoma (Part 2A), Randomized BMS-986218 Monotherapy Cohort Expansion (Part 2B), and Combination Cohort Expansions (Part 2C and Part 2D)**

Procedure	Cycle 1 (28 Days in Length) (Visit Window $\pm$ 2 Days, except for C1D1)				Cycle 2 (28 Days in Length) (Visit Window $\pm$ 2 Days)				Cycles 3 and Beyond (Each Cycle 28 Days in Length) (Visit Window $\pm$ 2 Days)	EOT a,b	Notes			
	DLT Period is Cycles 1 and 2													
	D1	D8	D15	D22	D1	D8	D15	D22	D1					
												of the infusion until completion of the infusion.  If any vital sign is abnormal (based upon clinician assessment) at the final check, the participant must be observed further for a period of time, as clinically indicated.		
Oxygen Saturation	X				X				X			Oxygen saturation to also be performed in conjunction with vital signs monitoring on these days. For all cycles after Cycle 3, vital signs and oxygen saturation are to be taken before the infusion and at the end of each infusion.		
ECG	X				X				X	X		ECGs should be recorded after the participant has been supine for at least 5 minutes and prior to blood draws. ECGs to be performed in triplicate in association with PK sampling, at predose and EOI, on Day 1 of both Cycle 1 and Cycle 3 for Part 1A only (see Section 9.1.3 ). Single safety ECGs to be performed for all other time points.		

**Table 2-2:**

**On-Treatment - Schedule of Activities for Q4W Dosing Schedules in BMS-986218 Monotherapy Escalation (Part 1A), Safety Evaluation of Combination Doses of BMS-986218 with Nivolumab (Part 1B), Randomized BMS-986218 Monotherapy Cohort Expansion in Cutaneous Melanoma (Part 2A), Randomized BMS-986218 Monotherapy Cohort Expansion (Part 2B), and Combination Cohort Expansions (Part 2C and Part 2D)**

Procedure	Cycle 1 (28 Days in Length) (Visit Window $\pm$ 2 Days, except for C1D1)				Cycle 2 (28 Days in Length) (Visit Window $\pm$ 2 Days)				Cycles 3 and Beyond (Each Cycle 28 Days in Length) (Visit Window $\pm$ 2 Days)	EOT a,b	Notes			
	DLT Period is Cycles 1 and 2													
	D1	D8	D15	D22	D1	D8	D15	D22	D1					
												Beyond Cycle 3, ECGs must be performed every 3 cycles up to EOT.		
Laboratory Tests	X	X	X	X	X	X	X	X	X	X		There will be a minus-72-hour window for collection of laboratory tests on Day 1 of each cycle and a window of $\pm$ 2 days for all other timepoints. Coagulation assessment at screening only. See Section 9.1.4 and Table 9.1.4-1 .		
Urinalysis		X			X					X		As clinically indicated; microscopic urine reflex only for urinalysis positive for blood/protein/leukocyte esterase		

**Table 2-2:**

**On-Treatment - Schedule of Activities for Q4W Dosing Schedules in BMS-986218 Monotherapy Escalation (Part 1A), Safety Evaluation of Combination Doses of BMS-986218 with Nivolumab (Part 1B), Randomized BMS-986218 Monotherapy Cohort Expansion in Cutaneous Melanoma (Part 2A), Randomized BMS-986218 Monotherapy Cohort Expansion (Part 2B), and Combination Cohort Expansions (Part 2C and Part 2D)**

Procedure	Cycle 1 (28 Days in Length) (Visit Window $\pm$ 2 Days, except for C1D1)				Cycle 2 (28 Days in Length) (Visit Window $\pm$ 2 Days)				Cycles 3 and Beyond (Each Cycle 28 Days in Length) (Visit Window $\pm$ 2 Days)	EOT a,b	Notes			
	DLT Period is Cycles 1 and 2													
	D1	D8	D15	D22	D1	D8	D15	D22	D1					
Pregnancy Test (WOCBP only)	X				X				X	X	Serum/urine to be collected within 24 hours prior to dosing. Pregnancy test may be completed on the first day of treatment, provided that the results are available before the start of study therapy. Serum or urine pregnancy test must be performed within 24 hours prior to administration of study treatment (urine pregnancy test: minimum sensitivity 25 IU/L or equivalent units of hCG).			
Adverse Event Reporting and Concomitant Medication Assessments														
Monitor for Non-SAEs	Non-SAEs will be collected starting with the first dose of study medication and through 100 days following the last dose of study treatment.									Section 9.2 and Appendix 3 . All AEs (SAEs or nonserious AEs) including those associated with SARS-CoV-2 infection must be collected continuously during the treatment period.				
Monitor for SAEs	All SAEs must be collected from the date of the participant's written consent until 100 days following the last dose of study treatment.									Section 9.2 and Appendix 3 .				
Concomitant Medications	X	X	X	X	X	X	X	X	X					

**Table 2-2:**

**On-Treatment - Schedule of Activities for Q4W Dosing Schedules in BMS-986218 Monotherapy Escalation (Part 1A), Safety Evaluation of Combination Doses of BMS-986218 with Nivolumab (Part 1B), Randomized BMS-986218 Monotherapy Cohort Expansion in Cutaneous Melanoma (Part 2A), Randomized BMS-986218 Monotherapy Cohort Expansion (Part 2B), and Combination Cohort Expansions (Part 2C and Part 2D)**

Procedure	Cycle 1 (28 Days in Length) (Visit Window $\pm$ 2 Days, except for C1D1)	Cycle 2 (28 Days in Length) (Visit Window $\pm$ 2 Days)		Cycles 3 and Beyond (Each Cycle 28 Days in Length) (Visit Window $\pm$ 2 Days)	EOT a,b	Notes					
	DLT Period is Cycles 1 and 2										
	D1	D8	D15	D22	D1	D8	D15	D22	D1	EOT a,b	Notes
PK Assessments											
Serial Blood Sampling	See Table 9.5-2 and Table 9.5-5 of the PK and immunogenicity sampling schedule and Section 9.5 .										
Immunogenicity (ADA) Assessments	See Table 9.5-2 and Table 9.5-5 of the PK and immunogenicity sampling schedule and Section 9.5.										

**Table 2-2:**

**On-Treatment - Schedule of Activities for Q4W Dosing Schedules in BMS-986218 Monotherapy Escalation (Part 1A), Safety Evaluation of Combination Doses of BMS-986218 with Nivolumab (Part 1B), Randomized BMS-986218 Monotherapy Cohort Expansion in Cutaneous Melanoma (Part 2A), Randomized BMS-986218 Monotherapy Cohort Expansion (Part 2B), and Combination Cohort Expansions (Part 2C and Part 2D)**

Procedure	Cycle 1 (28 Days in Length) (Visit Window $\pm$ 2 Days, except for C1D1)	Cycle 2 (28 Days in Length) (Visit Window $\pm$ 2 Days)		Cycles 3 and Beyond (Each Cycle 28 Days in Length) (Visit Window $\pm$ 2 Days)	EOT a,b	Notes					
	DLT Period is Cycles 1 and 2										
	D1	D8	D15	D22	D1	D8	D15	D22	D1	EOT a,b	Notes
Imaging Assessments											
Body Imaging	
Tumor imaging assessment to be performed Q8W from first dose (<math>\pm</math> 1 week), prior to initiating next cycle of treatment (for Part 1A, Part 1B, Part 2B, Part 2C, and Part 2D).
 
Tumor imaging assessment to be performed at 12 weeks from the first dose, regardless of dose delays, if any (<math>\pm</math> 1 week), prior to initiating the next cycle of treatment, for participants in the Randomized BMS-986218 Monotherapy Cohort Expansion in Cutaneous Melanoma (Part 2A). After that, subsequent tumor imaging assessments to be performed Q8W (<math>\pm</math> 1 week), prior to initiating the next cycle of treatment.
 
Participants who remain free of subsequent therapy will undergo tumor imaging assessment Q8W (<math>\pm</math> 1 week) until subsequent tumor-directed therapy is initiated or until 48 weeks after discontinuation of study treatment/EOT visit, and then Q12W (<math>\pm</math> 2 weeks) for a total duration of 2 years.
							
The same imaging modality is to be used for all assessments, per RECIST v1.1 (Appendix 5) or per PCWG 3 criteria for prostate (Appendix 12). Tumor assessment to be performed prior to initiating next cycle of treatment. CT and MRI scans should be acquired with slice thickness of 5 mm or less with no intervening gap (contiguous). Every attempt should be made to image each participant using an identical acquisition protocol on the same scanner for all imaging timepoints.
			
Brain Imaging	
Participants with history of brain metastasis will have MRI performed as clinically indicated and at the discretion of the Investigator.
							
MRI without and with contrast of the brain should be performed. CT of the brain without and with contrast may be obtained if MRI is contraindicated. CT and MRI scans should be acquired with slice thickness of 5 mm or less with no intervening gap (contiguous). Every attempt should be made to image each participant using an identical acquisition protocol on the same scanner for all imaging timepoints.
			

**Table 2-2:**

**On-Treatment - Schedule of Activities for Q4W Dosing Schedules in BMS-986218 Monotherapy Escalation (Part 1A), Safety Evaluation of Combination Doses of BMS-986218 with Nivolumab (Part 1B), Randomized BMS-986218 Monotherapy Cohort Expansion in Cutaneous Melanoma (Part 2A), Randomized BMS-986218 Monotherapy Cohort Expansion (Part 2B), and Combination Cohort Expansions (Part 2C and Part 2D)**

Procedure	Cycle 1 (28 Days in Length) (Visit Window $\pm$ 2 Days, except for C1D1)	Cycle 2 (28 Days in Length) (Visit Window $\pm$ 2 Days)		Cycles 3 and Beyond (Each Cycle 28 Days in Length) (Visit Window $\pm$ 2 Days)	EOT a,b	Notes		
	DLT Period is Cycles 1 and 2							
	D1	D8	D15	D22	D1	D8	D15	D22

**Table 2-2:**

**On-Treatment - Schedule of Activities for Q4W Dosing Schedules in BMS-986218 Monotherapy Escalation (Part 1A), Safety Evaluation of Combination Doses of BMS-986218 with Nivolumab (Part 1B), Randomized BMS-986218 Monotherapy Cohort Expansion in Cutaneous Melanoma (Part 2A), Randomized BMS-986218 Monotherapy Cohort Expansion (Part 2B), and Combination Cohort Expansions (Part 2C and Part 2D)**

Procedure	Cycle 1 (28 Days in Length) (Visit Window $\pm$ 2 Days, except for C1D1)	Cycle 2 (28 Days in Length) (Visit Window $\pm$ 2 Days)		Cycles 3 and Beyond (Each Cycle 28 Days in Length) (Visit Window $\pm$ 2 Days)	EOT a,b	Notes			
	DLT Period is Cycles 1 and 2								
	D1	D8	D15	D22	D1	D8	D15	D22	D1

**Table 2-2:**

**On-Treatment - Schedule of Activities for Q4W Dosing Schedules in BMS-986218 Monotherapy Escalation (Part 1A), Safety Evaluation of Combination Doses of BMS-986218 with Nivolumab (Part 1B), Randomized BMS-986218 Monotherapy Cohort Expansion in Cutaneous Melanoma (Part 2A), Randomized BMS-986218 Monotherapy Cohort Expansion (Part 2B), and Combination Cohort Expansions (Part 2C and Part 2D)**

Procedure	Cycle 1 (28 Days in Length) (Visit Window $\pm$ 2 Days, except for C1D1)				Cycle 2 (28 Days in Length) (Visit Window $\pm$ 2 Days)				Cycles 3 and Beyond (Each Cycle 28 Days in Length) (Visit Window $\pm$ 2 Days)	EOT a,b	Notes			
	DLT Period is Cycles 1 and 2													
	D1	D8	D15	D22	D1	D8	D15	D22						
Clinical Treatment Supplies														
BMS-986218 Administration	X				X				X		Study treatments, BMS-986218 and nivolumab, to be supplied by BMS; vials assigned by IRT must be used.			
Nivolumab Administration (Part 1B, 2C, and 2D only)	X				X				X					

Abbreviations: ADA = anti-drug antibody; AE = adverse event; BMS = Bristol-Myers Squibb; CXDY = Cycle X, Day Y, as an example; CT = computed tomography; D = day; DLT = dose-limiting toxicity; ECG = electrocardiogram; ECOG = Eastern Cooperative Oncology Group; EOI = end of infusion; [REDACTED]

EOT = end of treatment; [REDACTED]

hCG = human chorionic gonadotropin; [REDACTED]

IRT = Interactive Response Technology; MRI = magnetic resonance imaging; PCWG 3 = Prostate Cancer Working Group 3; PE = physical examination; PK = pharmacokinetic; Q8W = every 8 weeks; Q12W = every 12 weeks; [REDACTED]

[REDACTED] RECIST = Response Evaluation Criteria in Solid Tumors; SAE = serious adverse event; SARS-CoV-2 = severe acute respiratory syndrome coronavirus 2; WOCBP = women of childbearing potential.

a EOT is defined as the visit where the decision is made to discontinue the participant from treatment. Evaluations will be performed prior to study discharge, or for participants who are prematurely discontinued.

b For participants who complete all scheduled cycles of therapy, the EOT visit will be the same as the last scheduled and completed on-treatment visit (eg, Cycle 3 Day 21) and the start of the Safety Follow-up period. For participants who do not complete all scheduled cycles of therapy, the EOT visit will be the most recent on treatment visit (with all available safety and response data); it does not need to be repeated and will be considered as the start of the Safety Follow-up period.

**Table 2-3: On-Treatment - Schedule of Activities for Q2W Dosing Schedules in BMS-986218 Monotherapy Escalation (Part 1A)**

Procedure	Cycle 1 (28 Days in Length) (Visit Window ± 2 Days, except for C1D1)				Cycle 2 (28 Days in Length) (Visit Window ± 2 Days)				Cycles 3 and Beyond (Each Cycle 28 Days in Length) (Visit Window ± 2 Days)	EOT a,b	Notes		
	DLT Period is Cycles 1 and 2												
	D1	D8	D15	D22	D1	D8	D15	D22	D1 & D15				
Safety Assessments													
ECOG Performance Status	X		X		X		X		X	X			
PE	X		X		X		X		X	X			
Symptom Directed PE		X		X		X		X					
Weight	X		X		X		X		X	X			
Vital Signs	X	X	X	X	X	X	X	X	X	X	
For BMS-986218, vital signs will be obtained within 30 minutes before the start of the infusion and then every 15 minutes (± 5 minutes) from the start of the infusion until 60 minutes after completion of the infusion for the first 3 doses of study treatment on C1D1, C1D15, and C2D1. For all doses after C2D1, vital signs and oxygen saturation are to be taken before the infusion and at the end of infusion.
 
If any vital sign is abnormal (based upon clinician assessment) at the final check, the participant must be observed further for a period of time, as clinically indicated.
		

**Table 2-3: On-Treatment - Schedule of Activities for Q2W Dosing Schedules in BMS-986218 Monotherapy Escalation (Part 1A)**

Procedure	Cycle 1 (28 Days in Length) (Visit Window $\pm$ 2 Days, except for C1D1)				Cycle 2 (28 Days in Length) (Visit Window $\pm$ 2 Days)				Cycles 3 and Beyond (Each Cycle 28 Days in Length) (Visit Window $\pm$ 2 Days)	EOT a,b	Notes			
	DLT Period is Cycles 1 and 2													
	D1	D8	D15	D22	D1	D8	D15	D22	D1 & D15					
Oxygen Saturation	X		X		X		X		X			Oxygen saturation to also be performed in conjunction with vital signs monitoring on these days. For all infusions after C2D1, vital signs and oxygen saturation are to be taken before the infusion and at the end of each infusion.		
ECG		X		X		X		X		X		ECGs should be recorded after the participant has been supine for at least 5 minutes and prior to blood draws. ECGs to be performed in triplicate in association with PK sampling, at predose and EOI, on Day 1 of both Cycle 1 and Cycle 3 for Part 1A only (see Section 9.1.3 ). Single safety ECGs to be performed for all other time points. Beyond Cycle 3, ECGs must be performed every 3 cycles up to EOT.		
Laboratory Tests	X	X	X	X	X	X	X	X	X	X		There will be a minus-72-hour window for collection of laboratory tests on Day 1 of each cycle and a window of $\pm$ 2 days for all other timepoints. Coagulation assessment at screening only. See Section 9.1.4 and Table 9.1.4-1 .		

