- Complete blood counts and chemistry (including liver enzyme) tests will be performed prior to administration of study therapy and on a weekly basis during the first 8 weeks of treatment in monotherapy and the first 8 weeks of the combination between BMS-986218 and nivolumab. In addition, complete physical examinations (PEs) will be conducted on Day 1 of each new cycle, along with weekly symptom-directed targeted PEs during the first 8 weeks of treatment. Due to the potential risk of exaggerated inflammatory response, participants with autoimmune disorders or chronic viral infections, or those who are at risk for flare of auto-immunity or immune-related diseases will be excluded.

For the proposed clinical studies of BMS-986218, the overall risk for participating in these trials will also be minimized.

- The amount of blood sampling poses limited risk to the participant and includes discomfort, pain, and bleeding. The amount of total blood is reduced to the minimal quantity required to address the need of safety monitoring, standard of care, PK/anti-drug antibodies (ADAs), [REDACTED] needs and is below the recommended daily limits for each treatment day.

Whether BMS-986218 both as a single agent and in combination with nivolumab administration increases the risk for contracting severe acute respiratory syndrome coronavirus 2 (SARS-CoV-2) infection or increases the severity or duration of symptoms is currently unknown. This unknown risk must be considered when enrolling a participant.

No additional safety monitoring or routine screening tests will be required due to the SARS-CoV-2 pandemic. Participants with recent or acute infections will be excluded or delay start of treatment as defined in [Section 6.2](#). If a participant has a confirmed SARS-CoV-2 infection while on study treatment, dose delay or interruption of study treatment is required as described in [Section 7.6](#).

The study has been designed with study visits that allow for close monitoring of participants' safety throughout the clinical trial ([Section 2](#)), and participants are encouraged to contact the investigator if an intercurrent illness develops between study visits. Testing for COVID-19 to inform decisions about clinical care during the study should follow local standard practice.

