### **5.1.2 Treatment Period**

The dosing regimens of BMS-986218 are Q4W and Q2W. All participants will be treated with BMS-986218 Q4W ± nivolumab Q4W for up to 2 calendar years, BMS-986218 Q2W for up to 2 calendar years, and/or ipilimumab Q3W for up to a maximum of 4 doses. Each cycle of the treatment period will be 4 weeks in length, with the exception of the treatment arms with Q3W dosing of ipilimumab in the Randomized BMS-986218 Monotherapy Cohort Expansion in Cutaneous Melanoma (Part 2A), for which each cycle of ipilimumab will be 3 weeks in length. Continuous safety evaluation and tumor assessment for participants receiving BMS-986218 or nivolumab will guide the decision to treat a participant with additional cycles of study therapy if the participant has confirmed clinical benefit (up to a maximum of 2 calendar years for BMS-986218 Q4W ± nivolumab Q4W; or up to a maximum of 2 calendar years for BMS-986218 Q2W). Tumor assessments will occur every 8 weeks (Q8W) for participants receiving BMS-986218 and nivolumab for all study parts, except the Randomized BMS-986218 Monotherapy Cohort Expansion in Cutaneous Melanoma (Part 2A), where tumor assessment in participants receiving BMS-986218 or ipilimumab will occur at 12 weeks from first dose (± 1 week), prior to initiating the next cycle of treatment. After that, subsequent tumor imaging assessments to be performed Q8W (± 1 week), prior to initiating the next cycle of treatment.

Participants who remain free of subsequent therapy will undergo tumor imaging assessment Q8W ( $\pm$  1 week) until subsequent tumor-directed therapy is initiated or until 48 weeks after discontinuation of study treatment/EOT visit, and then Q12W ( $\pm$  2 weeks) for a total duration of 2 years.

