Weekly study visits will be performed for the first 8 weeks following the first dose of study treatment for the BMS-986218 Monotherapy Escalation (Part 1A), Safety Evaluation of Combination Doses of BMS-986218 with Nivolumab (Part 1B), the Randomized BMS-986218 Monotherapy Cohort Expansion in Cutaneous Melanoma (Part 2A), the Randomized BMS-986218 Monotherapy Cohort Expansion (Part 2B), the BMS-986218 Combination Therapy Cohort Expansion in NSCLC (Part 2C) and the BMS-986218 Combination Therapy Cohort Expansion in microsatellite stable colorectal cancer (MSS CRC) (Part 2D) followed by study visits Q4W thereafter. During Cycle 1 and Cycle 3 of the treatment period, additional study visits to collect samples for intensive PK, ADA, and cytokine assessments are required. See [Section 9.5](#) for further details.

In the BMS-986218 Monotherapy Escalation (Part 1A), the Randomized BMS-986218 Monotherapy Cohort Expansion in Cutaneous Melanoma (Part 2A), and the Randomized BMS-986218 Monotherapy Cohort Expansion (Part 2B), BMS-986218 will be administered Q4W. An alternative BMS-986218 dosing schedule of Q2W (with dosing on Day 1 and Day 15 of each 28-day cycle) will also be explored for monotherapy escalation using data obtained from the Q4W schedule. BMS-986218 will be infused over 30 minutes, except in the low-dose cohorts where infusion times may be shorter. BMS-986218 will require a 60-minute observation period following the completion of the infusion for the first 3 doses for each participant. Ipilimumab will be administered Q3W and will be infused over 30 minutes.

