### **7.6.3 Dose Delays Due To Toxicity**

Participants who experience the following due to any cause must have all study treatment(s) withheld:

- Potential DLTs, until DLT relatedness is defined.
- Select AEs and laboratory abnormalities:
  - $\geq$  Grade 2 pneumonitis.
  - $\geq$  Grade 2 abnormality in AST, ALT, or total bilirubin.
  - $\geq$  Grade 2 creatinine.
  - $\geq$  Grade 2 diarrhea or colitis.
  - $\geq$  Grade 2 neurological AE.
  - AE, laboratory abnormality, or concurrent illness that, in the judgment of the Investigator, warrants delaying study treatment administration.
  - Confirmed SARS-CoV-2 infection.

Criteria for participants who are required to permanently discontinue study treatments is listed in [Section 8.2](#). Participants not meeting guidelines for permanent discontinuation will be permitted to resume therapy based on the criteria specified below in Section 7.6.3.1. Participants eligible to resume study therapy will resume study therapy at the nominal treatment visit following their last received study medication dose.

The end of cycle tumor assessments, such as CT, magnetic resonance imaging (MRI), or positron emission tomography (PET), will continue on a Q8W schedule relative to the participant's first dose, regardless of any treatment delay incurred.

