### **9.1.4 *Clinical Safety Laboratory Assessments***

- Investigators must document their review of each laboratory safety report.
- A local laboratory will perform the analyses and will provide reference ranges for these tests. Results of clinical laboratory tests performed on Day -1 must be available prior to dosing.
- The laboratory tests that will be performed for study participants are shown in [Table 9.1.4-1](#).
- Results of all laboratory tests required by this protocol must be provided to the Sponsor, recorded either on the laboratory pages of the CRF or by another mechanism as agreed upon between the Investigator and BMS (eg, provided electronically). If the units of a test result differ from those printed on the CRF, the recorded laboratory values must specify the correct units. Any abnormal laboratory test result considered clinically significant by the Investigator must be recorded on the appropriate AE page of the CRF.

[figure not shown]

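### In the Q2W schedule (Table 2-3) the Day 15 safety labs may be drawn after the Day 15 infusion, which does not fit the protocol's lab-based hold and resume rules

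*Combined protocol and SAP*

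**What the plan says.** - **Table 2-3, Laboratory Tests.** Labs are scheduled on Days 1, 8, 15 and 22 in Cycles 1 and 2, and on Days 1 and 15 from Cycle 3. The note gives a "minus-72-hour window for collection of laboratory tests on Day 1 of each cycle and a window of $\pm$ 2 days for all other timepoints".
- **Section 5.1.2 and the administration row of Table 2-3.** Q2W treatment is given "with dosing on Day 1 and Day 15 of each 28-day cycle".
- **Section 3.3.** Among the risk-minimisation measures: "Complete blood counts and chemistry (including liver enzyme) tests will be performed prior to administration of study therapy". The same sentence goes on to weekly testing for the first 8 weeks.
- **Section 7.6.3.** "Participants who experience the following due to any cause must have all study treatment(s) withheld". The list includes Grade 2 or worse AST, ALT, total bilirubin and creatinine. Section 7.6.3.1 makes resumption after Grade 2 AST, ALT or bilirubin depend on the values being back at baseline.
- **Section 9.1.4.** "Results of clinical laboratory tests performed on Day -1 must be available prior to dosing". This is the only rule on when results must be available.

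**The concern.** The lab note is the one used in Table 2-2 (Q4W) and Table 2-4 (ipilimumab Q3W). There it is harmless, because every dose falls on Day 1. In the Q2W table, Day 15 is a dosing day that falls under the two-sided window for other timepoints.

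A site can therefore keep to Table 2-3 and infuse on Day 15 without a current result. The participant's transaminases, bilirubin or creatinine may by then already meet the protocol's own hold rule. The study is first-in-human. Section 3.2.1.3 reports the GI tract and kidney as the most severely and consistently affected organs in monkeys, with AST and ALT rises that did not reverse at the higher doses, so these are relevant analytes. Up to about 72 DLT-evaluable participants are planned for Q2W escalation, and the PD cohort starts on Q2W.

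The gap looks like an oversight. The vital-signs note in Table 2-3 names Cycle 1 Day 15 as a dosing day, and Table 9.5-3 schedules predose PK samples on Day 15 of Cycles 1, 2 and 3. The lab note was not adapted in the same way.

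**Working it through.** The plan gives no figure to reproduce. The check counts doses and works out what the stated windows allow.

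**Inputs.** Doses on Days 1 and 15 of a 28-day cycle (Section 5.1.2); DLT period of 8 weeks (Section 7.6.1); maximum treatment of 2 calendar years (Section 5.1.2), taken as 104 weeks; lab windows from Table 2-3.

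**Share of doses affected.**
- DLT period: 8 / 4 = 2 cycles, with doses on study Days 1, 15, 29 and 43. Days 15 and 43 (28 + 15) are Day 15 doses: 2 of 4.
- Full duration: 104 / 4 = 26 cycles; 26 × 2 = 52 doses, of which 26 are Day 15 doses: 26 / 52 = 50%.

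**Permitted draw dates.** Day 15 − 2 = Day 13 to Day 15 + 2 = Day 17. With the dose on nominal Day 15, a draw later that day or on Day 16 or 17 follows the infusion and still complies.

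**Age of the latest earlier scheduled labs at a nominal Day 15 dose, if the Day 15 draw comes afterwards.**
- Cycles 1 and 2: the Day 8 labs, allowed from Day 6 to Day 10. Age is 15 − 10 = 5 to 15 − 6 = 9 days.
- Cycle 3 on: no Day 8 labs are scheduled, so the Day 1 labs are the latest, drawn from 72 hours before Day 1 up to Day 1. Age is 15 − 1 = 14 to 14 + 3 = 17 days.

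**Does another passage close the gap?**
- Section 9.1.4 names only Day −1. Table 2-1 runs screening from Day −28 to Day −1, and none of Tables 2-2 to 2-4 has a Day −1 column. Read literally, the rule reaches the first dose at most.
- Section 3.3 can be read as labs before each dose, or as a test before treatment starts and then weekly tests. On the first reading Table 2-3 conflicts with it; on the second it is silent about Day 15.
- Sections 7.6.3 and 7.6.3.1 act on lab values but do not say when those values must be obtained relative to the dose.

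**The case against.** The strongest reply is that the protocol has other controls. Labs and dosing share the Day 15 column, so the lab window may simply mirror the ± 2-day visit window. Predose PK blood is drawn on Day 15 of Cycles 1 to 3, so a safety sample could be taken then. Section 7.3 ties treatment modification to laboratory criteria, and Section 9.1.4 requires investigators to document review of each report. In Cycles 1 and 2 a Grade 2 value on Day 8 would already trigger the hold.

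Much of this stands as mitigation. Many sites will draw before the infusion, and in the first 8 weeks the remaining exposure is mainly an abnormality that is new since Day 8. But none of these passages orders Day 15 safety labs before the dose. From Cycle 4, Table 9.5-3 schedules no Day 15 PK draw either.

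Four stronger readings are tempting, and the documents do not support them:
- **Section 3.3 promises labs before every dose.** It does not clearly say so; the sentence allows both readings above.
- **DLT data are compromised.** Section 7.6.1 assesses DLTs per participant over a 56-day period, and the model uses DLTs from that period. Nothing assigns a DLT to one infusion, so the count does not depend on whether a Day 16 or 17 finding began before or after the Day 15 dose.
- **Prior labs may be 11 or 19 days old.** Those figures count to Day 17, the last permitted draw date. They are ages at dosing only if the infusion itself slips to Day 17, which is not the case examined here.
- **Half of Q2W doses will be given without current labs.** The window permits this; nothing shows that sites will do it or that participants will stay on treatment for two years.

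**Conclusion.** The point holds as an inconsistency confined to the Day 15 visit of the Q2W schedule in Part 1A, including Q2W participants in the PD cohort. As written, Table 2-3 permits Day 15 labs after the Day 15 infusion, which does not serve the mandatory lab-based hold and resume rules. It also contradicts Section 3.3 if that section means labs before each dose.

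The share of doses is an upper bound: it assumes the full treatment duration and a draw after the infusion every time. The lab ages assume a dose on nominal Day 15 and no unscheduled tests. The gap is widest from Cycle 3, when weekly labs have stopped. No sample size, power or DLT-model result is affected.

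**What to change.** Reconcile the Table 2-3 lab note with Sections 3.3, 7.6.3, 7.6.3.1 and 9.1.4 for the Day 15 dosing visit. The collection window on Q2W dosing days should then be consistent with the protocol's own Day 1 window and hold rules. In doing so, the sponsor should state whether Section 3.3 means labs before each dose or before the start of treatment. Separately, reconcile the Day −1 reference in Section 9.1.4 with the visits that exist in the schedules.

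Section 9.1.4 applies to every study part and every scheduled test, so any rewording there should be checked for effects outside the Q2W schedule. Which results must be in hand before an infusion is a clinical decision for the sponsor.

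The cost is small. Aligning the Table 2-3 window adds no visit or sample and changes no dose, hold threshold or DLT criterion. Sites lose the option of drawing Day 15 labs after the infusion.
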